IRBNet ID: **1638783**

Title: **SEdative-Hypnotic Deprescribing Assisted by a Technology-Driven Insomnia InterVEntion (SEDATIVE)**

eRA Commons ID: **RX003732-01A1**

Funding Agency: **VA Rehabilitation Research & Development Service**

Principal Investigator: **[name]**

Version Date: **v.7 01/24/2023**

Summary

Chronic insomnia is one of the most common health problems among Veterans and significantly impacts their health, function, and quality of life. Sedative-hypnotic medications are the most common treatment despite mixed effectiveness and are associated with numerous risks that can further impact Veteran function. The Clinician Operated Assistive Sleep Technology (COAST) is an efficient, scalable, and adaptable digital platform that can help providers to reach more Veterans and provide evidence-based care for insomnia that translates to improved health and function. COAST delivery of cognitive behavioral therapy for insomnia (CBT-I) will be combined with Clinical Pharmacist-led sedative-hypnotic deprescribing to integrate two previously siloed interventions to deliver efficient evidence-based care.

This is a non-randomized, single group clinical trial:

- Aim 1:** To assess the feasibility of recruiting Veterans with chronic sedative-hypnotic use to participate in a 12-week combined deprescribing and CBT-I intervention, delivered through the COAST digital platform.
- Aim 2:** To assess Veteran acceptability and usability of the COAST platform.
- Aim 3:** To assess change in Veteran sleep, sedative-hypnotic use, and function pre- to post-intervention.

List of Abbreviations

BBTI	brief behavioral treatment for insomnia
BSC	Behavioral Sleep Clinic
CBT-I	cognitive behavioral therapy for insomnia
CDA	Career Development Award
CDW	Corporate Data Warehouse
CIWA	Clinical Institute Withdrawal Assessment Scale - Benzodiazepines
COAST	Clinician Operated Assistive Sleep Technology
Co-I	co-investigator
COVID-19	coronavirus disease 2019
CPP	Clinical Pharmacy Practitioner
C-SSRS	Columbia-Suicide Severity Rating Scale
GDR	gradual dose reduction
HIPAA	Health Insurance Portability and Accountability Act
HSR&D	Health Services Research and Development
ID	identification
IIR	investigator initiated research
ISI	Insomnia Severity Index
ISSO	information system security officer
M	mean
N/A	not applicable
NWAK	number of awakenings
PCMHI	Primary Care Mental Health Integration
PI	principal investigator
PROMIS	Patient-Reported Outcomes Measurement Information System

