The Insomnia Severity Index (ISI) will serve as the primary sleep outcome. The ISI is a brief measure of nighttime sleep disruption (e.g., severity of sleep onset) and daytime impact (e.g., interference with function).⁶⁰ The ISI is 7-items (0-4) with higher scores indicating greater severity or impairment. Total score (0-28) is categorized: no insomnia (0-7); sub-threshold (8-14); moderate (15-21); and severe insomnia (22-28). A reduction pre- to post-treatment ≥ 8 points indicate a treatment response and a post-treatment score ≤ 7 indicate remission. The ISI will be assessed at T₀, T₁, T₂ as well as weekly during treatment.

Sedative-hypnotic medication will be measured by participant self-report, as part of a daily entry in COAST (e.g., “What sleep medication and dose did you take today?”). The daily COAST entry will also involve assessments for adverse effects and/or withdrawal symptoms (i.e., Clinical Institute Withdrawal Assessment – Benzodiazepines [CIWA-B]). Outcomes will include post-treatment (T₁) medication dosage, relative to starting dose at baseline (T₀), and binary outcomes of $\geq 50\%$ reduction (yes/no) and total cessation (yes/no). Also, medication information from participants’ VA health records will be used to help validate their self-report of sedative-hypnotic use throughout the study. Additional information will be collected from the VA electronic health records (e.g., medical and psychiatric diagnoses, service utilization [e.g., insomnia-related care, behavioral health/sleep medicine appointments, sleep medicine pharmacy data]).

Additional *sleep* outcomes will be measured with a daily sleep diary.⁶¹ Sleep diaries provide information about a participant’s sleep behaviors, such as bedtime, rise time, total time in bed (TIB), total sleep time (TST), sleep onset latency (SOL), number of nighttime awakenings (NWAK), duration of wake after sleep onset (WASO), and sleep efficiency (SE). Sleep diaries will be completed daily from baseline (T₀) through post-treatment (T₁) and for 7-days at 3-month follow-up (T₂). Daily sleep diary data is used by COAST’s algorithms to generate personalized recommendations for each participant.

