Audio-recorded qualitative interviews will help to gain more nuanced information on COAST usability/acceptability. The interviews will be interpreted using the rapid qualitative inquiry^{66,67} to ensure that results are delivered in a timely manner to be meaningful to the study. Interviews will be summarized by the study's qualitative analyst into a template of categories that reflect topics of interest. The summaries will be coded by two analysts to develop the basis of content and thematic analyses.

Aim 3. Veteran clinical and functional outcomes will be evaluated with an ITT approach. We will fit mixed effects linear models that test change pre-post treatment (ISI, sleep diary, PROMIS) that includes a main effect of time (T_0-T_1 , T_0-T_2 , and T_1-T_2) and includes random effects for the Veteran (multiple measurements during treatment). Sedative-hypnotic change will be a determined by an ITT approach and fitting a mixed methods logistic model that tests for dose reduction ($\geq 50\%$, yes/no) and cessation of medication (yes/no) over the

course of treatment that includes a main effect of time (T_0-T_1 , T_0-T_2 , and T_1-T_2) and random effects for the Veteran. Additional analyses will compare completers vs. non-completers and responders vs. non-responders.

The study data analyst/statistician will lead quantitative analyses and the study qualitative analyst will lead qualitative analyses. The PI and Co-Is will also be involved in study analyses and interpretation.

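### Aim 3 diary model: Veteran random effects with no Veteran-by-time term and no averaging of nights would, fitted in the ordinary way on nightly rows, understate the standard error of change

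*Combined protocol and SAP*

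**What the plan says.** Section 5.3, Aim 3, sets out one model form for three kinds of outcome: "We will fit mixed effects linear models that test change pre-post treatment (ISI, sleep diary, PROMIS"). The fixed part is given by "that includes a main effect of time", with contrasts T0-T1, T0-T2 and T1-T2. The random part is given by "includes random effects for the Veteran (multiple measurements during treatment").

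Section 5.1 (Assessments) sets the data density:

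- Diary: "Sleep diaries will be completed daily from baseline" through post-treatment, then "for 7-days at 3-month follow-up".
- ISI: at T0, T1 and T2, "as well as weekly during treatment".
- Hierarchy: "The Insomnia Severity Index (ISI) will serve as the primary sleep outcome". The diary measures are additional sleep outcomes.

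The documents do not say whether the random effects go beyond an intercept, what the residual covariance is, or how degrees of freedom are obtained. They do not say whether nights are averaged, or which nights make up T0 and T1.

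**The concern.** A Veteran random intercept removes differences in level between Veterans. It does not remove differences in how much they change. If change varies, nights from the same Veteran in the same period remain correlated after the intercept is fitted. Extra nights then shrink the model's standard error of mean change as if they were extra Veterans.

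Unequal change is to be expected here. The tapers are individual, the CBT-I recommendations are tailored, and section 5.3 itself plans to compare responders with non-responders.

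At stake are the p-values and confidence intervals for change in sleep latency, wake after sleep onset, total sleep time, sleep efficiency and awakenings. Hypothesis H3 claims significant improvement in sleep behaviors, and section 5.3 says the results will feed into the design of a larger trial. The ISI is exposed only if its weekly scores are pooled as repeated rows.

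**Working it through.** **The plan's own figure.** Section 5.3 gives no standard error or type I error for this model. Its one figure is 95% power at effect size 0.65 with 37 completers (50 × 0.75 = 37.5). A paired t test at two-sided 5% (alpha and test are assumed, since neither is stated) has noncentrality 0.65 × √37 = 3.95 and power 97.0%. The point below does not depend on this figure.

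**Inputs.** From the documents: n = 37 completers, and 7 nights at T2. Assumed: the same 7-night window at T0 and T1 (m = 7), night-level SD σ = 1, SD of true individual change τ from 0 to 1.0 (in units of σ), no night-to-night autocorrelation, two-sided 5%.

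**Formulas, T0 against T1.**

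- Correct variance of mean change: (τ² + 2σ²/m)/n = 2M/(mn), where M = σ² + mτ²/2 is the expected Veteran-by-time mean square.
- The random-intercept model pools M (n − 1 = 36 df) with the night-within-period variance σ² (2n(m − 1) = 444 df). The pooled residual is s² = wM + (1 − w)σ², with w = 36/480 = 0.075. Its variance of mean change is 2s²/(mn).
- SE ratio r = √(s²/M).
- Rejection rate under no mean change ≈ 2[1 − Φ(1.96 r)].

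| τ/σ | M | s² | r | Rejection rate |
|---|---|---|---|---|
| 0 | 1.000 | 1.000 | 1.00 | 5% |
| 0.3 | 1.315 | 1.024 | 0.88 | 8% |
| 0.5 | 1.875 | 1.066 | 0.75 | 14% |
| 0.75 | 2.969 | 1.148 | 0.62 | 22% |
| 1.0 | 4.500 | 1.263 | 0.53 | 30% |

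Simulation of 8,000 trials per setting gave 8.4%, 13.7%, 21.9% and 29.7% for the last four rows. A t test on one mean per Veteran per period stayed at 4.7% to 5.1%.

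**Sensitivity.**

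- *Autocorrelation.* With a first-order night-to-night correlation of 0.2, simulated rates run from about 10% (τ = 0) to about 32% (τ = σ).
- *Window length.* With 14 nights, w = 36/998 = 0.036. The formula gives 12%, 22%, 35% and 44% at τ/σ of 0.3, 0.5, 0.75 and 1.0. The size of the error therefore depends on a window that the plan leaves open.
- *One score per time point.* With m = 1 the night-within-period df are zero, so w = 1 and r = 1. The random-intercept model with two times is then the paired t test.
- *Three single scores.* With equal correlations the error rate is about 5%. If the T1-T2 correlation is 0.6 to 0.8 against 0.4 for the other pairs, T0-T1 is 6% to 8%, while T1-T2 is 0.4% to 2%, which is conservative.
- *Weekly ISI rows.* With unmodelled slopes whose SD is 0.5 to 1.5 of the residual SD, the rate is 6% to 12%.

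**The case against.** The strongest reply is that the harm needs two conditions and section 5.3 states neither. The random effects are plural, so a slope is not ruled out. Nightly rows are an inference: time is defined by three points, and one averaged window per point would fit the text. The parenthesis about multiple measurements may only explain why a Veteran effect is there at all. This stands as far as it goes. A reader might infer that the plan commits itself to an intercept-only model on nights; it does not. But the random effects are tied to repeated measurements during treatment, the diary is nightly, and nothing provides for averaging or for Veteran-specific change. A random intercept on repeated rows is the ordinary way to carry out that text.

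Three other strong readings are not supported:

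- *That a main effect of time is itself too little.* "This is a non-randomized, single group clinical trial", so there is no arm for time to interact with. Time is the right fixed effect for change; the gap is in the random part.
- *That all Aim 3 inference, including the primary sleep outcome, is inflated.* With one score per time point, error for T0-T1 is nil to small, and T1-T2 can err the other way.
- *That the larger trial will be sized on these diary intervals.* Section 5.3 says only that the findings will inform its design, and its power statement rests on the ISI.

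It is also right that the size of the inflation rests on assumed variance components and starts from 5%. In the balanced case the point estimate of change is unaffected.

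**Conclusion.** The point holds in conditional form, for the diary outcomes and for the ISI only if weekly scores are pooled. The ordinary fit of the stated model takes nights as replicates and gives standard errors of change that are too small. For 37 Veterans, 7-night windows and no autocorrelation, the standard error is 1.0 down to about 0.53 of the correct value, and the false-positive rate is 5% up to about 30%. The upper end needs individual change to vary as much as single nights do. At half that SD the rate is about 14%. The window length at T0 and T1 and the variance ratio are assumptions, so this is a range and not a forecast. The change should be made, but it does not touch the primary sleep outcome analysed at T0, T1 and T2.

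**What to change.** In section 5.3, Aim 3:

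1. State that each diary measure enters as one mean per Veteran over a defined 7-night window at T0, T1 and T2, and say which nights those are and how missing nights are handled.
2. Fit these means with the main effect of time as planned and a within-Veteran covariance that does not force equal correlations between the three times.
3. If nightly diary or weekly ISI rows are kept, add a Veteran-by-time (or slope) random effect and use small-sample degrees of freedom.

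This changes analysis wording only and needs no new data or procedures. The cost is wider confidence intervals for diary change. They widen by the amount that the random-intercept intervals would have been too narrow: a factor of 1.0 to about 1.9 (1/0.53) over the range above.

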3.0 Objectives

- Study Objectives**

Aim 1: To assess the feasibility of recruiting Veterans with chronic sedative-hypnotic use to participate in a 12-week combined deprescribing and CBT-I intervention, delivered through the COAST digital platform.

Aim 2: To assess Veteran acceptability and usability of the COAST platform.

Aim 3: To assess change in Veteran sleep, sedative-hypnotic use, and function pre- to post-intervention.

- Hypotheses**

H1: It will be feasible to recruit Veterans with chronic sedative-hypnotic use to participate in the intervention.

H2: Veterans will find the COAST platform acceptable and usable.

H3: Veterans will significantly improve their sleep behaviors and function and decrease their sedative-hypnotic use.

- Relevance to Veterans**

Chronic insomnia and sedative-hypnotic use are prevalent among Veterans. This study will test a digital health platform, COAST, to deliver a combined intervention to (1) reduce use of sedative-hypnotics and (2) improve sleep behaviors using evidence-based behavioral interventions (CBT-I). If successful, this may offer an efficient and effective treatment for Veterans as an alternative to the current standards of care in VA.

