5.3 Data Analysis

This study is focused on the feasibility of recruitment and participation, usability and acceptability of COAST, and estimates of change in Veteran sleep and sedative-hypnotic use. The findings from this SPiRE will inform the study design of a larger clinical trial (e.g., RR&D Merit). A meta-analysis of digital CBT-I (2016) found a hedge's g of 1.09 (95% CI 0.74-1.45) when evaluating pre-post change on the Insomnia Severity Index (or similar measures).⁵⁴ The only study, to date, using NOCTEM COAST found a pre-post Cohen d of 1.93 for the ISI.⁵⁶ While there are few studies specifically looking at CBT-I plus sleep medication deprescribing, they show large effect sizes for change on the ISI (Cohen d = 1.98-2.26).^{49,64,65} Given the estimates from prior work conducted, we can expect an effect size range for pre-post ISI between 1.09 and 2.26 with an average effect size of 1.73 (large effect sizes). Given 50 recruited and accounting for a 25% drop out (i.e., 37 completers), we will still have 95% power to be able to detect an effect size of 0.65.

Prior to analyses for each aim, participant characteristics will be evaluated with descriptive statistics (e.g., age, sex, race). Distributions will be examined for normality, outliers, and missing data. Continuous variables (means/SD) and categorical variables (frequency/percentage) will be reported.

Aim 1. Feasibility will be evaluated in two ways. The first is by participant recruitment—how many participants contact the coordinator, undergo the study screen, and provide consent. The second is by treatment participation—how many participants download and activate the COAST app, complete baseline assessments, engage in treatment beyond the initial recommendation, and complete the intervention. Chi-square analyses will be used to determine group differences (age, sex, race) in recruitment response and participation rates.

Aim 2. Usability and acceptability of COAST will be evaluated by the PSSUQ measure. Usability/acceptability will be measured early in treatment ($T_{0+1\text{-week}}$) and at post-treatment (T_1) as well as change over time ($T_1 - T_{0+1\text{-week}}$). Change will be assessed using an intent-to-treat (ITT) approach and fitting mixed effects linear models that tests change in usability/acceptability (change on PSSUQ scores over the course of treatment) that includes a main effect of time ($T_{0+1\text{-week}}$ to T_1) and random effects for the Veteran.

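### If T0 is an outcome row, the logistic model for dose reduction cannot estimate its contrasts with baseline, and relative dose has no named inferential analysis

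*Combined protocol and SAP*

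**What the plan says.** Section 5.1 (Assessments) lists three sedative-hypnotic outcomes: post-treatment "medication dosage, relative to starting dose at baseline", a yes/no outcome for a reduction of at least 50%, and a yes/no outcome for total cessation. The data come from a daily entry in the app. VA medication records help to validate the self-report. The sleep diary runs from T0 to T1 and then "for 7-days at 3-month follow-up".

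Section 5.3 (Aim 3) covers the two binary outcomes. It says "Sedative-hypnotic change will be a determined by an ITT approach" and "fitting a mixed methods logistic model that tests for dose reduction" and for cessation over the "course of treatment that includes a main effect of time". The contrasts T0-T1, T0-T2 and T1-T2 and random effects for the Veteran follow. The sentence before it gives the linear mixed models for ISI, sleep diary and PROMIS the same three contrasts. Relative dose appears in neither list.

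This is a stated focus of the study. Section 5.3 opens by naming "estimates of change in Veteran sleep and sedative-hypnotic use" among its aims and says that the findings will inform a larger trial. H3 in section 3.0 reads "Veterans will significantly improve their sleep behaviors and function and decrease their sedative-hypnotic use".

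**The concern.** In a linear model for ISI, T0 carries information because each participant has a measured score there. A reduction from the T0 dose is different: at T0 it is zero for everyone. If the analyst carries the linear-model layout over, as the shared wording invites, the T0 cell for a reduction of at least 50% is empty. Two of the three listed contrasts are then inestimable.

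The logistic model is the only inferential analysis that 5.3 names for sedative-hypnotic use. If its baseline contrasts fail, the analyst must choose the replacement estimate, the denominator and the cessation window after seeing the data. Those estimates are what the next trial is meant to use.

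**Working it through.** **Inputs from the documents.** 50 recruited and "accounting for a 25% drop out (i.e., 37 completers" (5.3): 0.75 × 50 = 37.5, taken as 37, so 50 − 37 = 13 without completion. Reported cessation rates of 27-80% (2.0 Introduction) are used only to set illustrative event counts. Entry requires use on at least 3 days a week (5.1, 5.2). The plan gives no power or event figure for the sedative-hypnotic model, so there is no figure to reproduce.

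**Assumed.** Event patterns at T1/T2 among 37 (both, T1 only, T2 only, neither): 8/2/2/25 (10 events at each visit, 27%) and 28/2/2/5 (30 events, 81%).

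**Step 1: the T0 cell.** With dose D at each visit, the event at visit t is (D0 − Dt)/D0 ≥ 0.5. At t = T0 this is 0/D0 = 0, so the answer is no for everyone, provided that the T0 row and the reference dose are the same non-zero measurement. For cessation the cell need not be empty. Use on 3 days a week leaves 7 − 3 = 4 of 7 days (57%) without a dose, and no cessation window is stated.

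**Step 2: the likelihood.** With a random intercept, p(i,t) = 1/(1 + exp(−(βt + σu))) and u standard normal. If every T0 value is no, T0 contributes 1/(1 + exp(β0 + σu)) for each participant. This rises towards 1 as β0 falls, whatever the other parameters are. The likelihood therefore has no maximum in β0, and T1 − T0 and T2 − T0 diverge. The random intercept does not prevent this.

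Profile log-likelihood with β0 held fixed (61-point Gauss-Hermite quadrature):

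| β0 | 10 of 37 | 30 of 37 |
|---|---|---|
| −2 | −46.082 | −39.760 |
| −6 | −36.523 | −31.277 |
| −15 | −33.867 | −29.521 |
| −30 and below | −33.724 | −29.482 |

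A third assumed pattern (0, 18 and 16 events at T0, T1 and T2) shows the divergence directly. As β0 goes from −2 to −10 to −30, the T1 − T0 log odds ratio goes from 2.2 to 9.9 to 29.8. T2 − T1 settles at −0.693, the value from a fit to T1 and T2 alone.

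**Step 3: what stays finite.** The likelihood-ratio tests of time are 30.6 and 94.2 on 2 df, and the model-implied T1 proportions are 0.270 and 0.811. The test only sets T1 and T2 against a rate that is zero by definition, so it does not measure a change from an observed baseline rate.

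**Step 4: the denominator.** Wilson interval: (p + z²/2n ± z√(p(1−p)/n + z²/4n²)) / (1 + z²/n), z = 1.96. For 10/50: (0.2384 ± 0.1173)/1.0768 = 11.2% to 33.0%.

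| Events | Completers (37) | All enrolled (50), missing = no | All enrolled (50), missing = yes |
|---|---|---|---|
| 10 | 27% (15.4-43.0) | 20% (11.2-33.0) | 23/50 = 46% (33.0-59.6) |
| 30 | 81% (65.8-90.5) | 60% (46.2-72.4) | 43/50 = 86% (73.8-93.0) |

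The last two columns assume that all 13 dropouts lack medication status, so 20-46% and 60-86% are the widest bounds under the planned dropout.

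**Step 5: relative dose.** In a simulation of percent change with n = 37 (those who stopped at exactly −100%, the others uniform over assumed ranges), t-interval coverage was 94.1-94.9% at 27% cessation and 91.4-92.7% at 80%. BCa bootstrap coverage was 94.7% and 94.8-95.1%. An ordinary interval is adequate unless many values sit at −100%.

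**The case against.** **The wording may mean an interval.** 5.3 speaks of change over the course of treatment, and 5.1 scores the outcomes relative to T0. T0-T1 could therefore name the period over which reduction is scored, and then there is no separation. This stands as a possibility. The shared wording with the linear models makes the outcome-row reading the natural one, but the text does not decide.

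**An empty cell is conditional.** A reader might infer that neither outcome can occur at T0 under any coding. The documents do not support that. If the reference dose is recorded separately from the T0 window, a participant with no dose in that window could count as reduced or stopped.

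**The harm is contained.** A reader might infer that the whole sedative-hypnotic analysis fails. It does not: the T1-T2 contrast and the proportions survive, an analyst would notice the empty cell, and no go/no-go rule depends on these contrasts. Software would still print a T0 contrast, but its value would reflect the convergence tolerance. A penalised or Bayesian fit would give a finite value set largely by the penalty or prior, and 5.3 names neither.

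**Descriptive summaries are promised.** 5.3 says that means with SD and frequencies with percentages will be reported, so it would be too strong to say that relative dose will go unreported. That sentence belongs to the steps before the aim analyses and gives no interval, denominator or missing-data rule.

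**Missing status may be below 13 of 50.** VA records hold medication data (5.1), and withdrawn participants may continue in follow-up (5.4). This stands, and the bounds above are a worst case.

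**Conclusion.** The point holds conditionally. On the natural reading of 5.3, with the T0 value as the non-zero reference dose, the T0-T1 and T0-T2 contrasts for a reduction of at least 50% have no finite maximum-likelihood estimate. The same is likely, but not certain, for cessation. The separation itself does not depend on the assumed event counts. They only set the illustrative figures, and the 27-80% range refers to cessation; a reduction of at least 50% should be at least as frequent.

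The practical size is the unsettled choice of estimate: 27% or 20% for 10 events, 81% or 60% for 30, with missing-status bounds up to 20-46% and 60-86%. For relative dose, which 5.1 defines at T1 only, the gap is the lack of a named inferential analysis. This should be fixed before analysis; it does not undermine the trial.

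**What to change.** Amend 5.3 as follows.

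1. State that T0 is only the reference for the two binary outcomes and is not an outcome row. State the window over which the T0 reference dose and cessation are scored.
2. Make the main sedative-hypnotic estimates the proportions with at least 50% reduction and with cessation at T1 and T2, with Wilson or exact 95% intervals on all enrolled participants. Use VA-record medication data and retained follow-up first to reduce missing status. Then state the rule for what is still missing, and show the missing = no and missing = yes bounds. Give completers as secondary.
3. Limit the logistic mixed model, or a McNemar test, to T1 against T2.
4. Summarise relative dose at T1 as percent change from T0 with a 95% interval. A bootstrap such as BCa is an option if many values lie at −100%. T2 is an optional extension. State how a change of medication during the taper, which 5.1 (Pharmacist-led Deprescribing) allows for, is scored.

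The cost is slightly more analysis text and no new data. Proportions on all enrolled with missing counted as no will be lower than completer proportions, for example 20% against 27%.
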